Study Adherence: To encourage compliance the following will occur: (1) at the Baseline Visit, subjects will be given a schedule of all remaining appointments; (2) at each visit the subjects will be given an appointment reminder card for the next visit; (3) reminder calls, texts and/or emails (per subject's preference) will be placed or sent the day before each visit; (4) subjects will be routinely reminded that regardless of their smoking status their data are valuable and important; and (5) regardless of smoking status, subjects will be compensated at each visit (described in the following). If a subject misses a visit, study staff will try to reach him/her by phone that day to reschedule for one to three days later. If that does not work, staff will contact the subject's designated 'contact person' (i.e., someone who does not live with the subject but knows how to get in touch). If a subject does not attend any visits after the screening visits, he/she will be labeled as a "drop" and replaced. If the subject discontinues from the study after randomization but before the final follow-up visit, he/she will be labeled an "*incomplete*" but not replaced. If a subject does not quit on their assigned quit date or relapses later, she/he will be encouraged to stay in the study and make another quit attempt; such that we will follow them for three months regardless of smoking status. Subjects who complete the four week follow-up period after quit date, regardless of smoking status, will be labeled a "*completer*" for the primary outcome and not replaced. Our sample size goal to sufficiently power the primary outcome is for 200 completers.

[figure not shown]

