#### B.4.8. Statistical Analysis

Randomization scheme: Our power calculation for the primary outcome specifies 100 males and 100 females. Since we expect approximately 25% drop-out before determination of the primary endpoint, we will over-enroll, approximately 125 of each sex. Thus we will build randomization tables for up to 150 male and 150 female potential enrollees. Each sex group will be randomized 1:1 to PRO vs. PBO. Since enrollment and randomization will occur over several years, we will employ a randomly permuted blocks allocation, rather than a simple random allocation, stratified by sex. This will reduce the possibility of a chance imbalance in treatment assignments, ensuring that we have treatment balance maintained within sex group consistently across the enrollment period. Block sizes of 4 and 6 will be used in a 1:1 ratio.

Primary outcome analyses: This addresses Hypothesis 1. Our primary outcome is the binary indicator of relapsed yes/no at the week 4 visit. An unadjusted assessment of the treatment effect will come from a logistic regression of this binary outcome on randomized treatment assignment, separately by sex. The sex-specific treatment effect will be considered statistically significant if the p-value is <0.025. All persons randomized and with a measured primary outcome at the week 4 visit will be included in this analysis, regardless of whether or not they ever took any of their assigned treatment (intent-to-treat analysis); persons with missed visits are discussed below. While we expect baseline covariates to be balanced across treatment groups due to the randomization, an adjusted assessment of the treatment effect will then be carried out by a logistic regression including the randomized treatment assignment and pre-specified adjusting covariates such as age, baseline progesterone, estradiol, baseline impulsivity measures, etc. This pre-specified list will be determined by the study team during the finalization of the protocol, prior to the first study enrollment. We expect these analyses to be somewhat conservative, since they do not explicitly account for the randomized permuted blocking (Matts and Lachin, 1988). An analysis that accounts for the blocking (such as a stratified Mantel-Haenzel test) cannot be generalized to include the adjustment for impulsivity measures, for example, which are a focus of this proposal.

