Handling missing outcomes: For persons who do not attend a week 4 visit, assessment of the primary outcome is not directly possible. During their week 5, study staff will attempt to contact them in order to collect by phone and/or email a self-reported recall of smoking status as of week 4; outcomes collected in this way will be denoted separately in the study database. The primary outcome analysis will be carried out once excluding these persons, once including those for whom we were able to obtain a self-reported recall outcome, and once where we conservatively assume all these persons relapsed as of their week 4 visit. Since 'missing at random' is a strong statistical assumption to make in the primary outcome analysis, we will also carry out descriptive analyses to see whether persons missing their week 4 visit differed in their baseline characteristics or treatment assignment from persons not missing their week 4 visit.

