**Data Analysis Plan.** Addressing Hypothesis 1: Our primary outcome is the binary indicator of relapsed yes/no at the week 4 visit. An unadjusted assessment of the treatment effect will come from a logistic regression of this binary outcome on randomized treatment assignment, separately by sex. The sex-specific treatment effect will be considered statistically significant if the p-value is <0.025. All persons randomized and with a measured primary outcome at the week 4 visit will be included in this analysis, regardless of whether or not they ever took any of their assigned treatment (intent-to-treat analysis); persons with missed visits are discussed below. While we expect baseline covariates to be balanced across treatment groups due to the randomization, an adjusted assessment of the treatment effect will then be carried out by a logistic regression including the randomized treatment assignment and pre-specified adjusting covariates such as age, baseline progesterone, estradiol, baseline impulsivity measures, etc. This pre-specified list will be determined by the study team during the finalization of the protocol, prior to the first study enrollment. We expect these analyses to be somewhat conservative, since they do not explicitly account for the randomized permuted blocking (Matts and Lachin, 1988). An analysis that accounts for the blocking (such as a stratified Mantel-Haenzel test) cannot be generalized to include the adjustment for impulsivity measures, for example, which are a focus of this proposal.

Hypotheses:

Hypothesis 1: For both males and females, a lower proportion of subjects randomized to PRO will relapse by 4 weeks after quit date compared to those randomized to PBO.

Hypothesis 2: For both males and females, subjects randomized to PRO will have more days to relapse compared to those randomized to PBO.

Hypothesis 3: There will be a sex difference in smoking relapse such that females, regardless of randomization assignment, will have fewer days to relapse compared to males.

Hypothesis 4: Impulsivity will be a stronger relapse predictor in females than males.

Hypothesis 5: Among those with higher levels of serum PRO the influence of impulsivity on smoking relapse will be damped.

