#### **D. QUALITY ASSURANCE**

Data collected via computer programs (EMAs and REDCap) will be monitored by the study coordinator by random inspection of completed forms, and any problems detected will be discussed with the PI. The Statistics Core ([name], Director) will analyze the data using the SAS program. In addition, the Statistics Core will provide support in developing data entry programs. Data analyses will be completed at the end of the study. For missing data: Persons who do not attend a week 4 visit, assessment of the primary outcome is not directly possible. During their week 5, study staff will attempt to contact them in order to collect by phone and/or email a self-reported recall of smoking status as of week 4; outcomes collected in this way will be denoted separately in the study database. The primary outcome analysis will be carried out after excluding these subjects, including those for whom we were able to obtain a self-reported recall outcome, where we conservatively assumed all these individuals relapsed as of their week 4 visit. Since 'missing at random' is a strong statistical assumption to make in the primary outcome analysis, we will also carry out descriptive analyses to see whether persons missing their week 4 visit differed in their baseline characteristics or treatment assignment from persons not missing their week 4 visit.

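### The week 4 primary analysis is run three ways without a ranking: measured-only is implied as decisive but never named, and the stated power does not fit 125 per sex with 25% loss

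*Combined protocol and SAP*

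**What the plan says.** **Protocol B.4.8, primary outcome analyses.** The unadjusted analysis is a logistic regression of week 4 relapse on treatment, separately by sex. Two sentences follow in sequence: "The sex-specific treatment effect will be considered statistically significant if the p-value is <0.025", and then "All persons randomized and with a measured primary outcome at the week 4 visit will be included in this analysis". The set is labelled intent-to-treat, and missed visits are deferred to later text.

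**Protocol B.4.8, handling missing outcomes.** For people who miss the week 4 visit, "The primary outcome analysis will be carried out once excluding these persons, once including those for whom we were able" to obtain a recalled self-report, and "once where we conservatively assume all these persons relapsed as of their week 4 visit". The paragraph then remarks that missing at random "is a strong statistical assumption to make in the primary outcome analysis" and adds a descriptive comparison of those who missed the visit with those who did not. It states no threshold and no ranking.

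**Sample size.** B.4.3 (Study Adherence) says: "Our sample size goal to sufficiently power the primary outcome is for 200 completers". B.4.7, repeated in the DSMP's power section, gives 80% power for 100 completers per sex, with 125 per sex enrolled to allow for about 25% drop-out.

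**DSMP.** Section C repeats the label: "regardless of whether or not they ever took any of their assigned treatment (intent-to-treat analysis); persons with missed visits are discussed below". The text it defers to is in section D: "The primary outcome analysis will be carried out after excluding these subjects, including those for whom we were able to obtain" a recalled outcome, and the same sentence goes on to assume that all these people relapsed.

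**The concern.** A confirmatory test needs one analysis set and one rule for missing outcomes, fixed before the data are seen. Here three versions carry the name of the primary outcome analysis. Nothing says which governs the claim for each sex, or what to report if one falls below 0.025 and another does not. A reader could defend measured-only from the paragraph that contains the rule. Another could defend missing=relapsed because the plan calls it conservative. A choice made after unblinding would be open to challenge as driven by the result.

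Two related defects concern the same set. The intent-to-treat label sits on a set from which about a quarter of randomized participants are expected to be absent. The power statement assumes 100 completers per sex, which 125 enrolled and 25% loss do not yield.

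**Working it through.** **Inputs from the documents.** Two-sided alpha 0.025 per sex; placebo relapse 66%; odds ratio 3.5; 1:1 allocation; 100 completers, so 50 per arm per sex (B.4.7); about 25% lost and 125 enrolled per sex (B.4.7, B.4.8).

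**1. The plan's power figure.**
- Placebo odds: 0.66/0.34 = 1.941. Divided by 3.5: 0.5546. Relapse on progesterone (PRO): 0.5546/1.5546 = 35.7%.
- Power = Φ[(d − 2.2414 × SE0)/SE1], with d the difference in rates, SE0 = √(2p̄(1−p̄)/n) and SE1 = √((p1(1−p1)+p2(1−p2))/n).
- With n = 50 and d = 0.3032: SE0 = 0.1000, SE1 = 0.0953, and (0.3032 − 0.2241)/0.0953 = 0.83. Power is 79.7%, so the stated 80% is reproduced for 100 completers.

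**2. Power at the planned enrolment.**
- Completers: 125 × 0.75 = 93.75 per sex, or 46.9 per arm. One hundred completers at 25% loss needs 100/0.75 = 133.3, so 134 per sex. At 125 per sex, 100 completers corresponds to 20% loss.
- Measured-only, n = 46.9: SE0 = 0.1033, SE1 = 0.0984, and (0.3032 − 0.2315)/0.0984 = 0.73. Power is 76.7%.
- Missing=relapsed, n = 62.5, 25% missing in each arm: the rates become 0.25 + 0.75 × 0.66 = 74.5% and 0.25 + 0.75 × 0.357 = 51.8%. Then d = 0.2274, SE0 = 0.0863, SE1 = 0.0839, and (0.2274 − 0.1934)/0.0839 = 0.41. Power is 65.7%.
- Measured plus recall: about 69-83% by simulation, depending on how often drop-outs relapse and how fully they report it.

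**3. How often the versions disagree.** 400,000 trials were simulated per scenario, with 62 randomized per arm, 25% binomial drop-out in both arms, and completers relapsing at 66% and 35.7%. The following are assumptions, because the documents do not give them: recall reaches half of the missing; 0% or 30% of their relapses go unreported; drop-outs relapse at 66%, 80%, 90%, 100% or their own arm's rate.

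| Comparison at p<0.025, per sex | Share of trials |
|---|---|
| Any two of the three versions differ | 17.9-23.5% |
| Measured-only and missing=relapsed differ | 15.4-15.6% |
| – only measured-only significant | 13.1-13.3% |
| – only missing=relapsed significant | 2.3% |

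The measured-only against missing=relapsed rows do not depend on the recall assumptions.

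**4. A single data set.** Take measured relapse of 33/50 on placebo and 21/50 on PRO: p = 0.016, significant. Add 12 placebo and 13 PRO non-attenders as relapsed (25 of 125, or 20% missing): 45/62 against 34/63, p = 0.031, not significant. The plan has no sentence that says which result stands.

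**5. The DSMP sentence.** B.4.8 separates the versions by repeating that the analysis is done once for each. DSMP section D drops that separation, so one analysis would exclude, include and impute the same people. B.4.8 shows what was meant, but section D cannot be programmed as written.

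**The case against.** The strongest reply is that B.4.8 nearly settles the matter. Model, threshold and analysis set follow one another, and the set sentence refers to the analysis that has just received the threshold. The sample size is set in completers. The missing-outcomes paragraph says the outcome cannot be assessed directly in non-attenders, keeps recalled values apart in the database, and ties missing at random to the primary analysis. On that reading the second and third versions are ordinary sensitivity analyses. This stands as the natural reading, and the point is worded accordingly. What it does not supply is the label: all three versions still share one name, and no rule covers disagreement.

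Stronger readings are tempting but unsupported:
- **That the 0.025 threshold governs all three versions, or that type I error is inflated.** The missing-outcomes paragraph states no threshold, and no passage permits success on whichever version is significant. Under equal drop-out and no treatment effect, each version alone holds 2.4-2.6%.
- **That unequal drop-out measures the harm.** The documents give no drop-out rates by arm, and naming a version would not remove such bias.
- **That the intent-to-treat label conceals the exclusion.** The sentence states its restriction openly, the same section gives the 25% loss, and the missing=relapsed version covers everyone randomized. The label is inaccurate, not misleading by design.

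It is also fair that the shortfall to 94 completers is a sample-size matter that would remain if a version were named. It belongs here because power has to be stated for the set that decides.

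**Conclusion.** The concern holds as a gap in specification. Measured-only is implied as decisive but not named, two further versions share the primary label with no rule for disagreement, and the DSMP copy cannot be executed. At the design effect with 25% missing in each arm, the three versions reach different conclusions in about 18-24% of trials per sex, given the assumed 50% recall; measured-only and missing=relapsed differ in about 15-16%. The intent-to-treat label does not fit a set expected to omit about 25% of those randomized. The stated 80% is correct for 100 completers, but at 125 per sex with 25% loss power is about 77% for measured-only and 66% for missing=relapsed. These figures rest on equal drop-out between arms and an odds ratio of 3.5 among completers. The gap should be closed before unblinding; it does not show that the implied analysis is invalid.

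**What to change.** Before unblinding:
1. In B.4.8 (both paragraphs) and DSMP sections C and D, state which single version decides both sex-specific 0.025 tests: measured-only, as the text implies, unless the sponsor justifies another. Label the other two as sensitivity analyses.
2. If measured-only is kept, describe the set as randomized participants with an observed week 4 outcome and remove the intent-to-treat label from it.
3. Rewrite the DSMP section D sentence to match B.4.8.
4. In B.4.7 and the DSMP power section, restate power for the chosen version at 125 per sex with 25% missing.

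**Cost.** These are wording changes, with no new data or visits. Keeping measured-only changes no analysis. If the sponsor wants 80% power at 25% missing, it takes 68 randomized per arm (136 per sex), within the 150 per sex allowed by the randomization tables. Choosing missing=relapsed instead gives about 66% power at 125 per sex and 75% at 150; 80% would need 85 per arm (170 per sex), beyond those tables.

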**Table 1. Timing of Study Procedures by Sex**

	Female Subjects	Male Subjects
Initial Phone Interview		Anytime
Screening Visit 1	Menstrual Cycle Days 1-7	Within 2 weeks of Phone Screen
Screening Visit 2		Within 3 days of Screening Visit 1
Baseline Visit	Within 3 days after LH Surge	Delay matched to Female Subject
Medication Start		8PM on day of Baseline Visit
Quit Date		7 days after Baseline Visit
Week 0		Day of Quit Date
Week 1-Week 11		Weekly
Medication End		Day of Week 11 Visit
Final Visit		12 Weeks after Quit Date

Weeks 0-12 (Visits 4-16): The Week 0 clinic visit will occur on the assigned quit date. Subjects will attend clinic visits on a weekly basis thereafter for twelve weeks. At weeks 0-4, week 8 and week 12 blood samples (hormone measurement) will be collected. Urine samples will be collected at all visits from all participants (pregnancy tests for females; and visual inspection of urine color to confirm compliance with taking study medication via riboflavin filler). At weeks 0-4, week 8 and week 12 urine will be saved for biochemical confirmation of smoking status via nicotine/cotinine levels. Subjects will also complete several forms and questionnaires (described below). Subjects will also return the medication bottle and unused medication, be given a new two-week supply and adverse events will be assessed. At Week 11, study medication will be discontinued. Finally, subjects will receive brief smoking cessation behavioral counseling (Appendix A). At the end of each visit subjects will be paid for their time. These visits will take approximately 30-45 minutes to complete.

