#### B.4.7. Sample Size & Power Analysis

We expect an approximate drop-out rate of 25% based on our current, more burdensome protocol within a sample of 18-40 year-old females. Therefore, we will enroll a total of 125 female and 125 male participants to ensure we have 100 per sex group to complete the 4 week follow-up for the primary outcome. Participants will be randomized 1:1 to PRO or placebo, separately by sex group, as described above. In our earlier work ([name] et al, 2008), the luteal quit group had a prevalence of 66% relapse at 30 days; this estimates the placebo group relapse rate for our proposed study. Based on a two-tailed Pearson chi-square test with alpha=0.025 for each sex group, a sample size of 100 completers per sex group will have 80% power to detect an odds ratio of 3.5 or higher for comparing smoking relapse prevalence in the placebo group to smoking relapse prevalence in the PRO group. We observed an odds ratio of 3.2 for follicular quit group relapse compared to luteal quit group relapse ([name] et al, 2008). Since our PRO group will receive substantially more progesterone than the typical natural female cycle, it is reasonable to expect a slightly larger odds ratio for PRO compared to placebo. Since the difference in progesterone levels between the male PRO group and the male PBO group will be larger than the difference between the female PRO group and the female PBO group (see Figure 5), we expect a larger odds ratio (hence higher power) for the male treatment comparison.

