Safety analyses: Adverse events will be quantified separately by sex and treatment groups and compared across treatment groups with Fisher's exact test (for binary events) or with chi-square test (for counts of events or event rates).

Secondary outcome analyses: These address Hypothesis 2. Our secondary outcomes include the binary indicator of relapsed yes/no at the week 12 visit, and days to relapse, as described above. The binary outcome will be analyzed as described for the primary outcome. Days to relapse will be analyzed using Kaplan-Meier

curves with a log-rank test comparing treatments (unadjusted) and Cox proportional hazards analysis (adjusted for other characteristics), both of which allow for loss-to-follow up via right censoring (Therneau and Grambsch, 2000), separately for the CA and PA definitions. Adjusting variables will be selected as described for the primary outcome. The proportional hazards assumption on the treatment effect will be examined and tested (Lin, Wei, and Ying, 1993; Grambsch and Therneau, 1994).

Other analyses: To address Hypothesis 3, we will pool the male and female data and test for an interaction between sex and treatment assignment in an adjusted Cox regression for the days to relapse outcomes. To address Hypothesis 4, we will test a baseline impulsivity by sex interaction in the logistic regressions for the binary outcomes and in the Cox regressions for the days to relapse outcomes. To address Hypothesis 5, we will test a baseline impulsivity by baseline serum progesterone interaction in the logistic regressions for the binary outcomes and in the Cox regressions for the days to relapse outcomes. While this study was designed to be powered for Hypothesis 1, rather than for these comparisons, these will be used to generate preliminary data and hypotheses for future research on sex differences in addiction treatment and impulsivity.

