#### **E. Regulatory Issues: Adverse Events, Serious Adverse Events, Collection and Reporting**

Adverse Events: An adverse event is any unwanted experience or event occurring during the course of a clinical trial. At each visit, either a research nurse or physician will query the participant and log side effects and other treatment emergent events since the past visit, recording their severity (mild, moderate, severe, life-threatening), what action was taken, and whether the symptoms are continuing or resolved. The study investigators will follow all AEs to the point of a satisfactory resolution. A study subject may be withdrawn from the study if the PI determines it is the best decision for protection of the safety of the subject. All AEs will be assessed to determine if they meet criteria for an SAE. AEs will be quantified separately by sex and treatment groups and compared across treatment groups with Fisher's exact test (for binary events) or with chi-square test (for counts of events or event rates). The event will be documented as to whether there is 1) no relationship between the study drug and the adverse event, 2) the adverse event is unlikely related to administration of the study drug, 3) the adverse event is possibly related to study drug administration, or 4) the adverse event is probably related to the administration of the study drug.

Serious Adverse Events (SAE): A serious adverse event is defined as an outcome that is 1) fatal or life-threatening, 2) significantly or permanently disabling or incapacitating, 3) requires or prolongs inpatient hospitalization, or 4) results in

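### The chi-square test planned for adverse event counts or rates makes no allowance for differences between people, so its false-positive rate can exceed the nominal level

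*Combined protocol and SAP*

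**What the plan says.** The safety paragraph of B.4.8 has two branches. AEs are tabulated by sex and treatment, then "compared across treatment groups with Fisher's exact test (for binary events"), or "with chi-square test (for counts of events or event rates"). DSMP section E repeats the second branch: "or with chi-square test (for counts of events or event rates").

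On data collection, section E has a nurse or physician at each visit "log side effects and other treatment emergent events since the past visit" and record "whether the symptoms are continuing or resolved". The visit schedule around Table 1 of the protocol reads: "Subjects will attend clinic visits on a weekly basis thereafter for twelve weeks".

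Neither section says whether the unit of the chi-square test is the event, the person-visit or the person. Neither mentions several events in one person, a person-time denominator, or a significance level for safety. The only stated level belongs to the primary outcome: "The sex-specific treatment effect will be considered statistically significant if the p-value is <0.025". B.4.7 gives the size: "we will enroll a total of 125 female and 125 male participants".

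**The concern.** Applied to event totals, a chi-square test treats each event as an independent draw from a Poisson process with one common rate. AE data seldom behave that way. Some people report many symptoms and others none, and people who leave early have less time in which to report anything. Either feature makes the variance of the arm totals larger than the test assumes, and the p-values are then too small.

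At stake is the credibility of any reported arm difference in AE counts or rates. B.3 says that chronic use of progesterone as a cessation aid has not yet been investigated, and B.4.5 cites earlier use of under one month. A spurious excess in one sex could therefore colour how later work reads the drug's tolerability.

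**Working it through.** The plan states no figure for this comparison, so there is none to reproduce.

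**Inputs from the documents**
- 125 people per sex, randomised 1:1 (B.4.7, B.4.8): about 62 per arm within a sex, 125 per arm if the sexes are pooled.
- Weekly visits from Week 0 to Week 12: 13 visits.
- About 25% drop-out before the primary endpoint (B.4.8).

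**Assumed, because the documents are silent**
- A two-sided 5% level.
- A mean of 0.2 to 3 events per person.
- φ, the ratio of variance to mean of events per person.

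**Step 1. False-positive rate of the test on event totals.** With totals A and B in equal arms, the statistic is (A − B)²/(A + B) on 1 degree of freedom. If the true variance is φ times the mean, the rejection rate under no arm difference is 2·[1 − Φ(1.96/√φ)].

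| φ | 1.96/√φ | False-positive rate |
|---|---|---|
| 1 | 1.960 | 5.0% |
| 1.1 | 1.869 | 6.2% |
| 1.25 | 1.753 | 8.0% |
| 1.5 | 1.600 | 11.0% |
| 2 | 1.386 | 16.6% |
| 3 | 1.132 | 25.8% |

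Simulation agrees (10,000 null trials per setting, negative binomial counts, 62 or 125 per arm, means 0.2, 1 and 3): 4.8–5.2% at φ = 1, 7.5–8.2% at 1.25, 10.3–11.7% at 1.5, 15.7–16.6% at 2 and 25.1–26.1% at 3. Sample size and mean rate make almost no difference.

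**Step 2. Do repeat events alone cause this?** No. With Poisson counts averaging 3 per person, the simulated rate stays near 5%. The excess needs variation between people, in propensity or in exposure.

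**Step 3. Can drop-out alone push φ above 1 for raw counts?** Let everyone have the same Poisson rate. Then φ = 1 + μ·Var(T)/E(T)², where T is follow-up time and μ the mean count. Suppose 75% are followed for 13 weeks (Baseline to Week 12) and 25% leave at a uniform time in the 5 weeks from Baseline to Week 4.
- E(T) = 0.75×13 + 0.25×2.5 = 10.375.
- E(T²) = 0.75×169 + 0.25×25/3 = 128.83.
- Var(T) = 128.83 − 10.375² = 21.19.
- Var(T)/E(T)² = 0.197.

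So φ is 1.20, 1.39 and 1.59 at means of 1, 2 and 3 events. The Step 1 formula gives about 7%, 10% and 12%. If the same 25% leave uniformly over all 13 weeks, Var(T)/E(T)² is 11.44/11.375² = 0.088, φ is 1.09, 1.18 and 1.27, and the rates are about 6%, 7% and 8%. Simulated, a rate test with person-time in the denominator removes this component (4.9–5.1%). It does not remove differences in propensity.

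**Step 4. Other readings of the chi-square test.**
- Person-visits in a 2×2 table, 62 per arm and 13 visits: about 5% at a within-person correlation of 0, 8% at 0.02, 12% at 0.05, 18–20% at 0.10 and 28–29% at 0.20.
- Persons grouped by number of events (0, 1, 2, 3 or more): 2.6–5.4%, even at φ = 3.
- A single event type counted at most once per person, with probability p: φ = 1 − p, below 1, so the test is conservative.

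**Step 5. Person-level alternatives.** Fisher's test on any event has a simulated rate of 1.0–4.1%. Comparing mean events per person with the between-person variance gives 4.3–5.6% across all 30 settings (two arm sizes, three means, five values of φ). That check shows that using between-person variance restores the level; the negative binomial model itself was not simulated.

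**The case against.** A reader might infer that the safety comparison as a whole will report false arm differences well above 5%. The documents do not support that, for four reasons.

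- **The size cannot be derived.** No AE rate, dispersion or safety level is given, and the result runs from nominal at φ = 1 to about 26% at φ = 3.
- **Independence is an inference from the test named.** The text does not fix the unit of analysis, and a chi-square test on persons grouped by event count keeps its level.
- **A lasting symptom is probably one AE.** Section E records whether symptoms continue and follows each AE to resolution. The rules list at the end of the document likewise opens and later closes an AE on depression scores. Sedation that persists for weeks would then not be counted once per visit.
- **Only one branch is touched.** The Fisher branch for binary events is already planned and is sound.

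It can be added that the 25% drop-out is an overall figure, not an arm difference, that a rate can carry a time denominator, and that no stopping boundary or decision rule uses these p-values.

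All of this stands, and it limits the point without removing it. A test on counts of events or on rates is most naturally a test on totals, not on persons grouped by count. Counting a lasting symptom once does not stop one person from having several different AEs. Overall drop-out, equal in both arms, is enough to raise φ for raw counts (Step 3). If a person-level chi-square test was meant, the plan has to say so.

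**Conclusion.** The point holds for the counts/rates branch only. Read as a test on event totals or rates, the planned chi-square test is anti-conservative whenever people differ in AE propensity and, on raw counts, whenever follow-up is unequal. At an assumed 5% level the false-positive rate roughly doubles at φ = 1.5 and triples at φ = 2, and it is nominal at φ = 1. The stated drop-out alone would put φ at about 1.2 to 1.6 for raw counts, if departures fall before Week 4 and the mean is 1 to 3 events per person. Both of those conditions are assumptions. Between-person differences in propensity would add to this by an amount that the documents do not let anyone estimate.

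The consequence is minor. The efficacy analyses do not use this test, and the person-level Fisher results stand beside it. It is still more than a missing detail, because the test that is named can mislead and a better one uses data already collected.

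**What to change.** In B.4.8 and in DSMP section E:

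- State that the main safety comparison is Fisher's exact test on the number of persons with at least one event.
- Replace the chi-square test on counts or rates with a negative binomial model, or Poisson regression with robust variance, with log person-time as offset, by sex and treatment.
- State the significance level for safety comparisons, or say that the p-values are descriptive.

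The cost is a sentence or two in each place. No new data are needed, since event dates and visit attendance are already collected. Intervals for event rates widen by about √φ: √1.5 = 1.22, or 22%, and √2 = 1.41, or 41%. That widening is the correct uncertainty, not a loss of information. The offset and the dispersion term are both needed, because the offset deals with unequal follow-up and the dispersion term with unequal propensity.
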